For all safety analyses, "final" for the Treatment Period shall refer to the last non-missing observation in the Treatment Period but no more than 45 days after the last dose of the study drug for safety variables. The "final" for the post-treatment follow-up period for safety variables

shall refer to the last non-missing observation greater than 45 days but no more than 20 weeks after the last dose of study drug.

Definition of Analysis Windows

To perform longitudinal data analysis, observations that are obtained after the first day of study drug administration will be assigned to an analysis “Week” associated with the Rx Days that are corresponding to the observations. Unless otherwise specified, efficacy observations and safety observations no more than 45 days after the last dose of study drug will be included in analyses for the treatment period. Safety observations later than 45 days, but no more than 20 weeks, after the last dose of study drug will be included for the post-treatment follow-up period safety analysis. The intervals presented below for each scheduled visit (Rx Days X through Y) include both Rx Days X and Y. The nominal day for each scheduled post-baseline visit is 7 times “X” where “X” is visit week number. For example, the nominal day for Week 12 visit is $7 * 12 = 84$.

For measurements that are planned to be collected at Weeks 12, 24, 48, 72, 96, 144, 192, 240, and 260, i.e. clinical laboratory tests, observations will be mapped to an analysis “Week” according to the following windows defined by Rx day.

Week 12	Rx Days 2 through 126
Week 24	Rx Days 127 through 252
Week 48	Rx Days 253 through 420
Week 72	Rx Days 421 through 588
Week 96	Rx Days 589 through 840
Week 144	Rx Days 841 through 1176
Week 192	Rx Days 1177 through 1512
Week 240	Rx Days 1513 through 1750
Week 260	Rx Days > 1750

For measurements that are planned to be collected at Weeks 12, 24, 48, 72, 96, 120, 144, 168, 192, 216, 240 and 260, i.e. Brain MRI, observations will be mapped to an analysis “Week” according to the following windows defined by Rx day.

Week 12	Rx Days 2 through 126
Week 24	Rx Days 127 through 252

Week 48	Rx Days 253 through 420
Week 72	Rx Days 421 through 588
Week 96	Rx Days 589 through 756
Week 120	Rx Days 757 through 924
Week 144	Rx Days 925 through 1092
Week 168	Rx Days 1093 through 1260
Week 192	Rx Days 1261 through 1428
Week 216	Rx Days 1429 through 1596
Week 240	Rx Days 1597 through 1750
Week 260	Rx Days > 1750

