For measurements that are planned to be collected at Weeks 4, 4n (n=2, 3, ...12), 52, 72, 96, 104, 120, 144, 156, 168, 192, 208, 216, 240 and 260, i.e. body weight and C-SSRS, observations will be mapped to an analysis "Week" according to the following windows defined by Rx day.

Week 4	Rx Days 2 through 42
Week 4n	Rx Days $7*((n-1)*4+2)+1$ through $7*(n*4+2)$
Week 52	Rx Days 351 through 434
Week 72	Rx Days 435 through 588
Week 96	Rx Days 589 through 700
Week 104	Rx Days 701 through 756
Week 120	Rx Days 757 through 924
Week 144	Rx Days 925 through 1050
Week 156	Rx Days 1051 through 1134
Week 168	Rx Days 1135 through 1260
Week 192	Rx Days 1261 through 1400
Week 208	Rx Days 1401 through 1484
Week 216	Rx Days 1485 through 1596
Week 240	Rx Days 1597 through 1750
Week 260	Rx Days > 1750

For safety assessments that are planned to be collected during post-treatment follow-up period, observations will be mapped to an analysis “Week” according to the following windows defined by RxEnd day.

Post-Treatment Week 20 $45 < \text{RxEnd Days} \leq 140$

If more than 1 observation is included in a visit time window, the non-missing observation closest to the nominal day will be used in analyses. If more than 1 observation occurs on the same day, the average will be calculated and used in analyses.

3.0 **Version History**

Table 1 SPP Version History Summary

Version	Date of Approval	Summary
1.0	10 Feb 2021	Initial version
2.0	30 Jul 2021	
 • Removed contents related to efficacy, biomarker analysis, PK analysis, and some safety sections to align with update SAP v2.0 for abbreviated CSR • Update TOC for abbreviated CSR

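### In the body-weight/C-SSRS window grid, Week 104 ends at Rx Day 756 instead of the midpoint 784, so C-SSRS values nearer Week 104 are labelled Week 120

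*SAP*

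**What the plan says.** SPP section 2.2.2 (Definition of Analysis Windows) assigns each post-baseline observation to an analysis week. "The nominal day for each scheduled post-baseline visit is 7 times" the week number, and the listed intervals "include both Rx Days X and Y".

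There are three grids: clinical laboratory tests, brain MRI, and a third for weeks running up to "52, 72, 96, 104, 120, 144, 156, 168, 192, 208, 216, 240 and 260, i.e. body weight and C-SSRS". In the third grid:

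- Week 96 is "Rx Days 589 through 700"
- Week 104 is "Rx Days 701 through 756"
- Week 120 is "Rx Days 757 through 924"

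The MRI grid has no Week 104. There, Week 96 is "Rx Days 589 through 756".

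If several observations fall in one window, "the non-missing observation closest to the nominal day will be used in analyses". SAP section 10.4.1 summarises C-SSRS both by visit and for the entire study. The SPP table list keeps this as Table 14.3__5.

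**The concern.** The Week 104 window stops 28 days after its nominal day, while the Week 120 window opens 83 days before its own. An assessment on Rx Day 757 is 29 days from Week 104, yet is reported as Week 120. No text in the SPP or SAP explains a cut so close to Week 104.

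Two routes in the protocol can put a C-SSRS in the affected band:

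- **Make-up assessments.** The COVID-19 text after the rating scales in protocol section 5.3.1.1 says a missed scale should be completed at the next onsite visit. Dosing visits are every 4 weeks, so a C-SSRS missed at Week 104 would be made up at Week 108. On schedule that is Rx Day 757, the first day labelled Week 120. If the subject also has a true Week 120 assessment, the closest-to-nominal rule drops the make-up value, and the subject has no Week 104 entry.
- **Premature-discontinuation visits.** Protocol section 5.4.1 and Appendix C require a C-SSRS at discontinuation. The study was terminated early, and these visits can fall on any Rx Day.

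At stake is the visit label, and so the content of the Week 104 and Week 120 rows, in a safety table that is still to be produced.

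**Working it through.** **Inputs**, all from SPP section 2.2.2 unless noted:

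- Nominal day = 7 × week: Week 96 = 672, Week 104 = 728, Week 120 = 840.
- Rx Day = date − first dose date + 1, so a visit exactly *w* weeks after first dose is Rx Day 7*w* + 1.
- Visit tolerance of ±4 days: protocol, Definition of Terms and Appendix C.

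**Step 1: find the rule behind the tables.** The SPP states no boundary rule. Try boundary = 7 × (w₁ + w₂) / 2, with the midpoint day itself going to the earlier visit.

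| Grid | Boundaries | Equal to midpoint |
|---|---|---|
| Laboratory | 8 | 8 |
| Brain MRI | 11 | 11 |
| Body weight/C-SSRS | 24 | 23 |
| Total | 43 | 42 |

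Examples: Week 72/96, 7 × (72 + 96) / 2 = 588, as stated. Week 96/104, 7 × (96 + 104) / 2 = 700, as stated.

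**Step 2: the exception.** Week 104/120: 7 × (104 + 120) / 2 = 784, against 756 stated. Difference: 784 − 756 = 28 days.

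**Step 3: what reproduces 756.** 7 × (96 + 120) / 2 = 756, which is the Week 96/120 boundary of the MRI grid. In the C-SSRS grid the lower cut for Week 104 (700) allows for the extra visit; the upper cut does not.

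**Step 4: which days are mislabelled.** For Days 757 to 783 (27 days), the distance to 728 is 29 to 55 days and the distance to 840 is 83 down to 57 days, so each is strictly nearer Week 104. Day 784 is 56 days from both; the grids' tie convention gives it to Week 104.

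**Step 5: scheduled visits.** Week 104 on schedule is Rx Day 729, or 725 to 733 with tolerance, inside 701–756. Week 108 on schedule is Rx Day 757, or 753 to 761 with tolerance, across the stated boundary. Appendix C schedules C-SSRS at Weeks 104 and 120 but at no visit between them.

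**The case against.** **No stated rule is broken.** The SPP never says that boundaries are midpoints, its windows are contiguous and can be programmed as written, and the closest-to-nominal rule applies only within a window. All of that is true. But 42 of 43 boundaries fit one rule, the exception fits the same rule with Week 104 left out, and nothing in the text supports a different cut. Carry-over from the MRI grid is a likely origin, but it remains an inference.

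**Little data can be affected.** This largely stands. On-time Week 104 and Week 120 assessments map correctly, so only late, make-up, unscheduled or discontinuation C-SSRS values matter. Body weight shares the grid and is collected every 4 weeks, but the SPP table list has no by-visit weight summary. The entire-study C-SSRS counts and the individual listing (Appendix 16.2__4.5.2) do not depend on the windows, and no between-group comparison of C-SSRS is planned.

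**The correction has a cost.** This also stands. Treatment-period data must lie within 45 days of the last dose. A last dose at Week 100 on schedule is Rx Day 701, at most 705, and 705 + 45 = 750, short of 757. So on schedule, anyone with an in-band value was dosed at Week 104 or later, when a C-SSRS was also due. If that assessment took place, a corrected window puts both values in Week 104, and the one near Day 729 is selected. The discontinuation value then leaves the by-visit table, where the present window shows it as Week 120.

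**A reader might try to count affected subjects**, for example by spreading discontinuation visits evenly from the original protocol date (09 April 2018) to SPP version 2.0 approval (30 July 2021): 28 / 1,208 = 2.3%. The documents do not support this. That span is not follow-up, since nobody was dosed on the protocol date. No first-dose dates, termination date or enrolled number are given, and even spread is an assumption.

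**Conclusion.** The Week 104/120 boundary in the body-weight/C-SSRS grid is inconsistent with every other boundary in the SPP and should be 784. The error is 28 days, of which 27 are strictly nearer Week 104 and one is a tie. This rests on reading the midpoint rule from the tables, since the SPP does not state it.

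The effect is minor and confined to the by-visit part of Table 14.3__5. A make-up C-SSRS at Week 108, or a discontinuation C-SSRS in the band, is shown under the wrong visit or displaced by a true Week 120 value. A reader might infer that scheduled visits or the overall suicidality findings are distorted; the documents do not support that. How many subjects have a C-SSRS in the band can be read only from the trial data.

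**What to change.** In the body-weight/C-SSRS grid of SPP section 2.2.2, and in the window code, set Week 104 to Rx Days 701 through 784 and Week 120 to Rx Days 785 through 924. Leave the MRI grid alone; 756 is correct there. If 756 was intended in the C-SSRS grid, the SPP should say why.

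The work is two numbers and a rerun of Table 14.3__5. The cost is that a discontinuation C-SSRS in this band, from a subject who also has an on-time Week 104 assessment, will no longer appear in the by-visit display. It stays in the entire-study summary and the listing. A table footnote saying so would be enough.

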10.4 Analysis for Other Safety Variables

10.4.1 Columbia-Suicide Severity Rating Scale (C-SSRS)

Number and percentage of subjects in the following categories will be summarized for each treatment group and overall subjects by visit and for the entire study:

- Answered 'Yes' to each C-SSRS item
- Had suicidal ideation (defined as answering 'Yes' to one or more suicidal ideation items)
- Had suicidal ideation only (defined as answering 'Yes' to one or more suicidal ideation items and answering 'No' to all suicidal behavior items)
- Had suicidal behavior (defined as answering 'Yes' to one or more suicidal behavior items)
- Had suicidal ideation or behavior (defined as answering 'Yes' to one or more suicidal ideation or behavior items)

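### The programming plan's closest-record rule makes no exception for C-SSRS, so by-visit counts can leave out what a discontinuation interview found (likewise MRI findings, if tabulated by visit)

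*SAP*

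**What the plan says.** SPP 2.2.2 sets out analysis windows and names the measurements they cover. One set of windows is for scans ("i.e. Brain MRI, observations will be mapped to an analysis" week) and another for weight and the suicidality scale ("i.e. body weight and C-SSRS, observations will be mapped to an analysis" week). The section closes with a general rule for windows holding more than one record: "the non-missing observation closest to the nominal day will be used in analyses". It adds: "If more than 1 observation occurs on the same day, the average will be calculated and used in analyses". Neither sentence is limited by type of data, and SAP 10.4.1 and 10.4.2 give no exception.

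SAP 10.4.1 summarizes C-SSRS items and derived categories "by visit and for the entire study". The SPP appendix shows that the follow-up C-SSRS form refers to the period since the last visit (Appendix 16.2__4.5.2). It also lists MRI tables of new micro-hemorrhages and ARWMC change since the last visit (Tables 14.3__6.3 and 6.4) and over time (6.5). SAP 10.4.2 describes baseline and post-baseline MRI findings and new lesions over the double-blinded period, without saying that any table is by visit.

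Laboratory values are treated differently. SAP 10.3.1 counts a subject with at least one qualifying observation at any point in the study.

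**The concern.** Keeping the record nearest the target day suits a level such as body weight, where either record estimates the same quantity. It does not suit answers about what happened since the previous assessment, because the retained record does not carry what the omitted one reported.

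The protocol's own schedule can produce two records in a window. The Week 260/PD column of Appendix C marks both C-SSRS and brain MRI. Section 5.4.1 also asks for C-SSRS promptly after discontinuation; MRI is not in that section's list, so the PD scan rests on Appendix C. The study ended early (SAP 9.1), so for many subjects the last on-treatment assessment is likely to be a PD visit. Safety is the primary objective, and a reader of a by-visit C-SSRS row would not see that a Yes at that visit had been set aside.

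**Working it through.** **Inputs**
- Nominal day = 7 × week (SPP 2.2.2). Check: 7 × 12 = 84, as printed for Week 12.
- Windows as printed. Every MRI upper bound equals the midpoint of adjacent nominal days. One C-SSRS bound does not (Week 104: 756 against 784); the printed value is used.
- Assessment weeks from protocol Appendix C. MRI at Weeks 72, 120 and 168 is optional.
- Assumptions: scheduled visits on Rx Day 7W + 1 (the first dose is Rx Day 1); all earlier scheduled assessments done; the PD visit on the four-week dosing grid about 28 days after the last dose, so inside the 45-day limit.

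**1. One case of each**
- C-SSRS, Week 52 window (Rx Days 351–434, nominal 364). Week 52 interview on Day 365: |365 − 364| = 1. PD interview at Week 56, Day 393: |393 − 364| = 29. The PD interview is omitted.
- MRI, Week 48 window (253–420, nominal 336). Week 48 scan on Day 337: distance 1. PD scan at Week 56, Day 393: distance 57. The PD scan is omitted.

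**2. All PD visits on the grid**

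The horizons are Rx Day 756, which gives Weeks 4 to 104 (26 visits), and Rx Day 1208, which gives Weeks 4 to 172 (43 visits). Day 1208 is only an upper limit: the days from the protocol date of 09 April 2018 to SPP version 2.0 on 30 July 2021.

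| Measure | PD weeks at which the PD record is omitted | To Day 756 | To Day 1208 |
|---|---|---|---|
| C-SSRS | 56, 60, 76, 80; then 124, 128, 148, 160, 172 | 4/26 = 15% | 9/43 = 21% |
| MRI, no optional scans | 16, 28, 32, 52, 56, 100, 104; then 148, 152 | 7/26 = 27% | 9/43 = 21% |

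In every such case the scheduled record lies 1 day from nominal and is kept.

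**3. PD on any day from Rx Day 2 to 756 (755 days)**
- C-SSRS: the 12 windows for Weeks 4 to 48 give 13 days each (156). Weeks 52, 72, 96 and 104 give 69, 83, 27 and 27. Total 362; 362/755 = 48%.
- MRI without the optional Week 72 scan: 41 + 83 + 83 + 83 = 290; 290/755 = 38%.
- Of the 362 C-SSRS days, 16 windows × 13 = 208 fall within 13 days of a scheduled interview.

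**4. Direction of error for C-SSRS**

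Take a kept and an omitted record, each with ideation Yes/No and behavior Yes/No: 16 patterns. Compared with combining both records:

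| Category | Under-counted | Over-counted |
|---|---|---|
| Ideation | 4 | 0 |
| Behavior | 4 | 0 |
| Ideation or behavior | 3 | 0 |
| Ideation only | 1 | 2 |

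The two over-counts arise because ideation-only requires "answering 'No' to all suicidal behavior items", and the omitted record held a behavior Yes.

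**5. MRI illustration.** If the kept scan shows 0 new micro-hemorrhages and the omitted one shows 2, the row shows 0 subjects and 0 lesions instead of 1 and 2.

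**The case against.** One record per window is a sound convention: it ties each row to a planned assessment and keeps extra visits from inflating counts. That stands for continuous variables, but it does not show where a Yes on the omitted interview is counted by visit.

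The size is easily overstated. The 48% in step 3 treats every day as equally likely for a PD visit, and 208 of its 362 days follow a scheduled interview by at most 13 days. Averaged over all 755 days, the omitted C-SSRS record covers only 10.3 days after the scheduled one. This stands, so the grid figures are the ones to quote. All of these are shares of hypothetical PD visits, not of subjects or events.

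COVID-19 deferral to the next onsite visit is a lesser route, because protocol 5.3.1.1 allows C-SSRS by phone or video.

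The SPP defines the final value, which "shall refer to the last non-missing observation in the Treatment Period but no more than 45 days after the last dose". That would capture a PD record, but no C-SSRS or MRI table is said to use it.

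A reader might infer three stronger things.
- That whole-period totals lose these events. The windows are introduced for a stated purpose ("To perform longitudinal data analysis, observations that are obtained after the first day of study drug administration" are assigned to weeks), so the entire-study C-SSRS and double-blinded-period MRI summaries most naturally use every record, though this is not written.
- That averaging a same-day Yes and No will corrupt the tables. Such an average (0.5) fits no category, but neither route yields two records on one day.
- That the MRI tables are certainly affected. By-visit presentation is only implied by their titles.

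**Conclusion.** The point holds as a minor one. For C-SSRS, a stated rule applied as written gives a wrong by-visit count whenever the omitted interview holds a Yes that the kept one lacks. For MRI the same follows only if Tables 14.3__6.3 to 6.5 are presented by visit.

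The illustrative shares of 15% to 21% of PD visits for C-SSRS and 21% to 27% for MRI rest on on-schedule visits, PD on the four-week grid and, for MRI, no optional scans. A PD assessment more than 45 days after the last dose is outside the treatment-period windows and is not affected. If a scheduled visit runs early, the PD record can be the one retained, and the scheduled record is then lost instead.

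Nothing here shows that a safety conclusion would change. No between-group comparison is planned (SAP 10.1), adverse event tables do not use these windows, and the listings and appendices keep all records.

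**What to change.** In SPP 2.2.2, restrict closest-to-nominal selection and same-day averaging to continuous variables. Then add:
- **C-SSRS:** count any Yes per item over all on-treatment records in the window, and derive ideation-only after combining.
- **MRI, if tabulated by visit:** count a finding present on any in-window scan, at its worst severity. Combine new lesions and ARWMC change across in-window scans in a way consistent with how scans are read. Say in SAP 10.4.2 whether the tables are by visit.
- **Whole-period summaries:** state that the entire-study C-SSRS and double-blinded-period MRI summaries use all post-baseline on-treatment records.

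The cost is a few lines of text and programming, with no new data. Deferred and unscheduled assessments would then contribute, so by-visit counts may rise slightly; a footnote can say so.

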4.0 Appendix

Table 22 List of tables and figures to be programmed

Table	Title
TABLE 14.1__1	SUBJECTS DISPOSITION (ALL ENROLLED SUBJECTS)
TABLE 14.1__2.1	ACCOUNTABILITY BY INVESTIGATOR (ALL ENROLLED SUBJECTS)
TABLE 14.1__2.2	SUMMARY OF REASONS FOR STUDY DISCONTINUATION (ALL ENROLLED SUBJECTS)
TABLE 14.1__2.3	SUMMARY OF REASONS FOR STUDY DRUG DISCONTINUATION (SAFETY DATA SET)
TABLE 14.1__2.4	LISING OF SUBJECTS WHO MISSED ≥ 3 STUDY DRUG INFUSIONS DUE TO COVID-19 PANDEMIC (Safety DATA SET)
TABLE 14.1__2.5	LISTING OF SUBJECTS NUMBERS, INVESTIGATIONAL SITE NAMES, AND VISIT INFORMATION FOR SUBJECTS WHO RECEIVED REMOTE VIRTUAL VISITS DUE TO COVID-19 PANDEMIC (SAFETY DATA SET)
TABLE 14.1__2.6	LISTING OF SUBJECTS NUMBERS, INVESTIGATIONAL SITE NAMES, AND VISIT INFORMATION FOR SUBJECTS WHO RECEIVED REMOTE VIRTUAL VISITS DUE TO COVID-19 PANDEMIC (SAFETY DATA SET)
TABLE 14.1__3.1	DEMOGRAPHIC CHARACTERISTICS - PART 1 (GENDER, RACE, ETHNICITY, AGE GROUPS AND BODY MASS INDEX GROUPS) (SAFETY DATA SET)
TABLE 14.1__3.2	DEMOGRAPHIC CHARACTERISTICS - PART 2 (AGE, WEIGHT, HEIGHT AND BODY MASS INDEX) (SAFETY DATA SET)
TABLE 14.1__3.3	DEMOGRAPHIC CHARACTERISTICS - PART 3 (ALCOHOL AND TOBACCO USE) (SAFETY DATA SET)
TABLE 14.1__4	SUMMARY OF BASELINE CHARACTERISTICS (ITT DATA SET)
TABLE 14.1__5.1	SUMMARY OF MEDICAL/SURGICAL HISTORY BY BODY SYSTEM AND CONDITION/DIAGNOSIS (SAFETY DATA SET)
TABLE 14.1__5.2	SUMMARY OF ALZHEIMER'S DISEASE HISTORY (SAFETY DATA SET)
TABLE 14.1__5.3	SUMMARY OF ALZHEIMER'S DISEASE FAMILY HISTORY (SAFETY DATA SET)
TABLE 14.1__6	SUMMARY OF PREVIOUS AND CONCOMITANT MEDICATION USE (SAFETY DATA SET)
TABLE 14.1__7.1	NUMBER OF SUBJECTS FOR STUDY DRUG INFUSIONS (SAFETY DATA SET)
TABLE 14.1__7.2	SUMMARY OF STUDY DRUG EXPOSURE (DAYS) (SAFETY DATA SET)
TABLE 14.1__7.3	SUMMARY OF MEAN VOLUME PERCENTAGE OF ADMINISTERED STUDY DRUG INFUSIONS (SAFETY DATA SET)

TABLE 14.1__7.4	SUMMARY OF TILOVANEMAB EXPOSURE AFFECTED BY COVID-19 PANDEMIC (SAFETY DATA SET)
TABLE 14.3__1.1	OVERVIEW OF TREATMENT-EMERGENT ADVERSE EVENTS AND ALL DEATHS (SAFETY DATA SET)
TABLE 14.3__1.2	NUMBER AND PERCENTAGE OF SUBJECTS WITH TREATMENT-EMERGENT ADVERSE EVENTS BY SYSTEM ORGAN CLASS AND PREFERRED TERM (SAFETY DATA SET)
TABLE 14.3__1.3	NUMBER AND PERCENTAGE OF SUBJECTS WITH TREATMENT-EMERGENT ADVERSE EVENTS ASSESSED BY THE INVESTIGATOR AS HAVING REASONABLE POSSIBILITY OF BEING RELATED TO STUDY DRUG BY SYSTEM ORGAN CLASS AND PREFERRED TERM (SAFETY DATA SET)
TABLE 14.3__1.4	SUBJECTS WITH TREATMENT-EMERGENT ADVERSE EVENTS BY SYSTEM ORGAN CLASS, PREFERRED TERM AND MAXIMUM RELATIONSHIP TO STUDY DRUG (SAFETY DATA SET)
TABLE 14.3__1.5	SUBJECTS WITH TREATMENT-EMERGENT ADVERSE EVENTS BY SYSTEM ORGAN CLASS, PREFERRED TERM AND MAXIMUM SEVERITY (SAFETY DATA SET)
TABLE 14.3__1.6	NUMBER AND PERCENTAGE OF SUBJECTS WITH TREATMENT-EMERGENT ADVERSE EVENTS BY PREFERRED TERM IN DESCENDING ORDER OF INCIDENCE (SAFETY DATA SET)
TABLE 14.3__1.7.1	LISTING OF SUBJECT NUMBERS ASSOCIATED WITH EACH PT FOR ALL TREATMENT-EMERGENT ADVERSE EVENTS (SAFETY DATA SET)
TABLE 14.3__1.7.2	LISTING OF SUBJECT NUMBERS ASSOCIATED WITH EACH PT FOR ALL TREATMENT-EMERGENT ADVERSE EVENTS ASSESSED BY THE INVESTIGATOR AS HAVING REASONABLE POSSIBILITY OF BEING RELATED (SAFETY DATA SET)
TABLE 14.3__2.1.1	NUMBER AND PERCENTAGE OF SUBJECTS WITH SERIOUS TREATMENT-EMERGENT ADVERSE EVENTS BY SYSTEM ORGAN CLASS AND PREFERRED TERM (SAFETY DATA SET)
TABLE 14.3__2.1.2	LISTING OF SERIOUS ADVERSE EVENTS (SAFETY DATA SET)
TABLE 14.3__2.2.1	NUMBER AND PERCENTAGE OF SUBJECTS WITH TREATMENT-EMERGENT ADVERSE EVENTS LED TO DISCONTINUATION OF STUDY DRUG BY SYSTEM ORGAN CLASS AND PREFERRED TERM (SAFETY DATA SET)
TABLE 14.3__2.2.2	LISTING OF ADVERSE EVENTS THAT LED TO DISCONTINUATION OF STUDY DRUG (SAFETY DATA SET)
TABLE 14.3__2.3.1	NUMBER AND PERCENTAGE OF SUBJECTS WITH FATAL ADVERSE EVENTS INCLUDING EATHS BY SYSTEM ORGAN CLASS AND PREFERRED TERM (SAFETY DATA SET)
TABLE 14.3__2.3.2	LISTING OF FATAL ADVERSE EVENTS (SAFETY DATA SET)
TABLE 14.3__2.4	LISTING OF SUBJECT DEATHS (SAFETY DATA SET)
TABLE 14.3__3.1	NUMBER AND PERCENTAGE OF SUBJECTS MEETING CRITERIA FOR POTENTIALLY CLINICALLY SIGNIFICANT HEMATOLOGY (SAFETY DATA SET)
TABLE 14.3__3.2	LISTING OF SUBJECTS MEETING CRITERIA FOR POTENTIALLY CLINICALLY SIGNIFICANT HEMATOLOGY (SAFETY DATA SET)
TABLE 14.3__4.1	NUMBER AND PERCENTAGE OF SUBJECTS MEETING CRITERIA FOR POTENTIALLY CLINICALLY SIGNIFICANT CHEMISTRY (SAFETY DATA SET)

TABLE 14.3__4.2	LISTING OF SUBJECTS MEETING CRITERIA FOR POTENTIALLY CLINICALLY SIGNIFICANT CHEMISTRY (SAFETY DATA SET)
TABLE 14.3__5	SUMMARY OF C-SSRS (SAFETY DATA SET)
TABLE 14.3__6.1	SUMMARY OF NUMBER AND PERCENTAGE OF SUBJECTS PERTAINING CEREBRAL EDEMA, MICRO- AND MACRO-HAEMORRHAGES, WHITE MATTER HYPERINTENSITIES (SAFETY DATA SET)
TABLE 14.3__6.2	NUMBER AND PERCENTAGE OF SUBJECTS WITH PRESENCE AND INCREASING SEVERITY OF CEREBRAL OEDEMA (SAFETY DATA SET)
TABLE 14.3__6.3	NUMBER AND PERCENTAGE OF SUBJECTS WITH NEW MICRO-HEMORRHAGES SINCE THE LAST VISIT (SAFETY DATA SET)
TABLE 14.3__6.4	NUMBER AND PERCENTAGE OF SUBJECTS WITH WHITE MATTER HYPERINTENSITIES CHANGE (ARWMC SCORE) SINCE THE LAST VISIT (SAFETY DATA SET)
TABLE 14.3__6.5	DESCRIPTIVE STATISTICS OF NUMBER OF NEW MICRO-HEMORRHAGES AND CHANGES OF ARWMC SCORES OVER TIME (SAFETY DATA SET)
TABLE 14.3__6.6	LISTING OF SUBJECTS WITH POST-BASELINE MRI FINDINGS (SAFETY DATA SET)
APPENDIX 16.2__1	STUDY AND STUDY DRUG COMPLETION
APPENDIX 16.2__2.1	INCLUSION/EXCLUSION CRITERIA
APPENDIX 16.2__2.2	PROTOCOL DEVIATIONS
APPENDIX 16.2__2.3	PREGNANCY TEST
APPENDIX 16.2__3	SUBJECTS EXCLUDED FROM THE EFFICACY ANALYSIS
APPENDIX 16.2__4.1	SUBJECT DEMOGRAPHICS
APPENDIX 16.2__4.2	SUBJECT MEDICAL/SURGICAL HISTORY
APPENDIX 16.2__4.3	TOBACCO AND ALCOHOL USE
APPENDIX 16.2__4.4	NEUROLOGICAL EXAMINATION
APPENDIX 16.2__4.5.1	COLUMBIA-SUICIDE SEVERITY RATING SCALE (C-SSRS - BASELINE) SCORE
APPENDIX 16.2__4.5.2	COLUMBIA-SUICIDE SEVERITY RATING SCALE (C-SSRS - SINCE LAST VISIT) SCORE
APPENDIX 16.2__4.6	ALZHEIMER'S DISEASE HISTORY
APPENDIX 16.2__5	STUDY DRUG ADMINISTRATION
APPENDIX 16.2__6.1	ADVERSE EVENTS

APPENDIX 16.2__6.2	SUBJECT DEATHS
APPENDIX 16.2__6.3	CONCOMITANT NON-AD MEDICATIONS AND SUPPLEMENTS
APPENDIX 16.2__6.4	SERIOUS ADVERSE EVENTS RELEVANT MICROBIOLOGY DATA
APPENDIX 16.2__6.5	SERIOUS ADVERSE EVENTS RELEVANT LABORATORY DATA
APPENDIX 16.2__6.6	SERIOUS ADVERSE EVENTS ADDITIONAL NON-PROTOCOL DIAGNOSTIC/THERAPEUTIC PROCEDURES
APPENDIX 16.2__7.1.1	HEMATOLOGY DETERMINATIONS - PART 1
APPENDIX 16.2__7.1.2	HEMATOLOGY DETERMINATIONS - PART 2
APPENDIX 16.2__7.1.3	HEMATOLOGY DETERMINATIONS - PART 3
APPENDIX 16.2__7.1.4	HEMATOLOGY DETERMINATIONS - COMMENTS AND VALUES OUTSIDE THE REFERENCE RANGE
APPENDIX 16.2__7.2.1	CHEMISTRY DETERMINATIONS - PART 1
APPENDIX 16.2__7.2.2	CHEMISTRY DETERMINATIONS - PART 2
APPENDIX 16.2__7.2.3	CHEMISTRY DETERMINATIONS - PART 3
APPENDIX 16.2__7.2.4	CHEMISTRY DETERMINATIONS - PART 4
APPENDIX 16.2__7.2.5	CHEMISTRY DETERMINATIONS - PART 5
APPENDIX 16.2__7.2.6	CHEMISTRY DETERMINATIONS - COMMENTS AND VALUES OUTSIDE THE REFERENCE RANGE
APPENDIX 16.2__7.3.1	URINALYSIS DETERMINATIONS - PART 1
APPENDIX 16.2__7.3.2	URINALYSIS DETERMINATIONS - PART 2
APPENDIX 16.2__7.3.3	URINALYSIS DETERMINATIONS - PART 3
APPENDIX 16.2__7.3.4	URINALYSIS DETERMINATIONS - COMMENTS AND VALUES OUTSIDE THE REFERENCE RANGE
APPENDIX 16.2__7.4	VITAL SIGNS
APPENDIX 16.2__7.5	ELECTROCARDIOGRAM TEST RESULTS
APPENDIX 16.2__7.6.1	MRI RESULTS
APPENDIX 16.2__7.6.2	VOLUMETRIC MRI RESULTS
APPENDIX 16.2__7.7	TAU PET IMAGING RESULTS

